1.2.2.2 Lerapolturev in patients with melanoma

Lerapolturev has been administered via intratumoral injection (1 x 10⁸ TCID₅₀ per lesion per visit) to 12 participants in a Phase 1 open-label study with unresectable and/or metastatic anti-PD-1 refractory melanoma (as defined by the investigator) as of 23 March 2021 (NCT03712358). No serious adverse events (SAEs) or dose-limiting toxicities (DLTs) were observed, and administration of 1 x 10⁸ TCID₅₀ lerapolturev to one lesion/visit

Confidential Page 37 of 109

for up to three successive visits was well tolerated. This included 5 participants that received 3 injections of lerapolturev who had received prior anti-PD-1 therapy within 30 days prior to administration of lerapolturev (and thus had anti-PD1 therapy on board during lerapolturev); none of these participants experienced systemic toxicities. All AEs were Grade 1 or 2 in severity (pruritis [58%] and erythema [50%]) and primarily localized to the injected lesion(s).

Based on the favorable tolerability profile, and encouraging preliminary anti-tumor activity (33% ORR per irRC) noted in Phase 1, this study (NCT04577807) was designed to test the safety and efficacy of lerapolturev alone or in combination with anti-PD-1 therapy, in participants with unresectable melanoma who meet the more rigorous and objective definition for anti-PD-1 resistance, as described in the SITC Immunotherapy Resistance Task Force Guidance⁷. Despite a 6-fold increase in the total maximum lerapolturev dose relative to Phase 1 (ie, 6 x 10⁸ TCID₅₀ versus 1 x 10⁸ TCID₅₀ in Phase 1) and/or injection of up to 6 lesions per treatment visit (compared to 1 lesion/visit in Phase 1), lerapolturev remains well tolerated, whether given alone or when combined with anti-PD-1 therapy. As summarized in Table 3 and Table 4, 17 participants were treated with lerapolturev monotherapy (n=11) or lerapolturev combined with anti-PD-1 therapy (n=6) as of the 10 December 2021 data cutoff. Additionally, 7 lerapolturev monotherapy participants crossed over to receive the lerapolturev/anti-PD-1 combination.

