Total number of treatment-related ³ serious AEs, n	0	0	0	0	0	0	0
Lerapolturev-related serious AEs, n	0	0	0	0	0	0	0
Anti-PD-1-related serious AEs, n	NA	NA	NA	0	0	0	0
Participants with one or more dose- limiting toxicities AEs, n (%)	0 (0.0%)	0 (0.0%)	0 (0.0%)	0 (0.0%)	0 (0.0%)	0 (0.0%)	0 (0.0%)
Participants with one or more Grade 3 or 4 AEs, n (%)	2 (33.3%)	0 (0.0%)	2 (18.2%)	1 (16.7%)	3 (17.6%)	1 (14.3%)	2 (15.4%)
Participants with any Grade 3 or 4 Treatment-related ³ AE, n (%)	0 (0.0%)	0 (0.0%)	0 (0.0%)	0 (0.0%)	0 (0.0%)	0 (0.0%)	0 (0.0%)
Lerapolturev-related Grade 3 or 4 AEs, n (%)	0 (0.0%)	0 (0.0%)	0 (0.0%)	0 (0.0%)	0 (0.0%)	0 (0.0%)	0 (0.0%)
Anti-PD-1-related Grade 3 or 4 AEs, n (%)	NA	NA	NA	0 (0.0%)	0 (0.0%)	0 (0.0%)	0 (0.0%)
Participants with one or more Grade 5 AEs, n (%)	0 (0.0%)	0 (0.0%)	0 (0.0%)	0 (0.0%)	0 (0.0%)	0 (0.0%)	0 (0.0%)

Confidential Page 39 of 109

Summary	Lerapolturev Monotherapy, Safety Run-in ¹ (N=6)	Lerapolturev Monotherapy (Arm 1) ¹ (N=5)	All Lerapolturev Monotherapy 1 (N=11)	Lerapolturev/ Anti-PD-1 (Arm 2) (N=6)	All Participants ¹ (N=17)	Crossover ² Lerapolturev Monotherapy to Lerapolturev/Anti- PD-1 (N=7)	All Lerapolture v/ Anti-PD-1 (N=13)
Participants with any Grade 5 treatment-related ³ AE, n (%)	0 (0.0%)	0 (0.0%)	0 (0.0%)	0 (0.0%)	0 (0.0%)	0 (0.0%)	0 (0.0%)
Lerapolturev-related Grade 5 AEs, n (%)	0 (0.0%)	0 (0.0%)	0 (0.0%)	0 (0.0%)	0 (0.0%)	0 (0.0%)	0 (0.0%)
Anti-PD-1-related Grade 5 AEs, n (%)	NA	NA	NA	0 (0.0%)	0 (0.0%)	0 (0.0%)	0 (0.0%)
Participants with one or more lerapolturev AESIs	0 (0.0%)	0 (0.0%)	0 (0.0%)	0 (0.0%)	0 (0.0%)	0 (0.0%)	0 (0.0%)
Participants with one or more AEs with an ISR	0 (0.0%)	0 (0.0%)	0 (0.0%)	0 (0.0%)	0 (0.0%)	0 (0.0%)	0 (0.0%)
Participants with one or more AEs with signs of CRS/ICANs	0 (0.0%)	0 (0.0%)	0 (0.0%)	0 (0.0%)	0 (0.0%)	0 (0.0%)	0 (0.0%)

AESI = adverse event of special interest; CRS = cytokine release syndrome; ICANS = immune effector cell associated neurotoxicity syndrome; ISR = injection site reaction; NA = not applicable; PD-1 = programmed cell death protein 1; AE = adverse event

Confidential Page 40 of 109

¹ Data shown do not include data collected during crossover.
² Crossover starts with first administration of first crossover cycle. Pooled data presented for all crossover participants.
³ Treatment-related based on definite, possible, and probable relatedness to lerapolturev and/or anti-PD-1.

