6.2 Treatment Beyond Progression

Evidence indicates some patients treated with immunotherapy may derive clinical benefit after initial evidence of apparent disease progression^{42,43}. Therefore, study drug administration may be continued until loss of clinical benefit, provided the participant appears to be deriving clinical benefit and the Investigator believes it is in the best interest of the participant to continue. Treatment past disease progression per RECIST 1.1 should only be considered if a participant is clinically stable and has the following:

- Evidence of clinical benefit as assessed by the Investigator; assessment of clinical benefit should take into account whether the participant is clinically deteriorating and unlikely to receive further benefit from continued treatment
- Absence of symptoms and signs (including worsening of laboratory values; eg, new or worsening hypercalcemia) indicating unequivocal progression of disease
- No decline in ECOG performance status that can be attributed to disease progression
- Absence of tumor growth at critical anatomical sites (eg, leptomeningeal disease)
 that cannot be managed by protocol-allowed medical interventions

Decisions to continue treatment beyond initial progression per RECIST 1.1 may be discussed with the medical monitor and should be documented in the study records.

Participants with radiographic disease progression confirmed at a subsequent tumor assessment (ie, iCPD) may be considered for continued study treatment at the discretion of the investigator if they continue to meet the criteria above and have evidence of clinical benefit.

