3.2.6. Definitions and Terminology

Age

Age is age at informed consent and is as captured on the eCRF.

CONFIDENTIAL Page 19 19 November 2024

Baseline Value

For purposes of analysis, the baseline value is defined as the last non-missing value obtained prior to initiation of study drug.

Cycle 1, Day 1 (Baseline)

Cycle 1, Day 1 is the earliest day that study drug is initiated.

Study Day

Study Day is defined relative to Baseline (Cycle 1, Day 1). Thus, the study day of an event is calculated as:

Study Day = event date – date of Cycle 1, Day 1 (+ 1, if event date \geq date of Cycle 1, Day 1).

Study Visit

Study Visit is the nominal visit as recorded on the eCRF.

Change from Baseline

Change from baseline for a given endpoint is defined as the Study Day X value minus the Baseline Value.

Days on Study

Days on study is the number of days from Cycle 1, Day 1 to the date of study completion as recorded on the End of Study eCRF page.

Adverse Event (AE)

An AE is any untoward medical occurrence in a patient or clinical study participant, temporally associated with the use of study drug(s), whether or not considered related to the study drug(s). An AE can therefore be any unfavorable and unintended sign (including an abnormal laboratory finding), symptom, or disease (new or exacerbated) temporally associated with the use of study drug(s).

Treatment-emergent Adverse Event (TEAE)

A TEAE is an AE that occurred during the study on or after the initiation of study drug through 30 days after last dose of study drugs. Additionally, it is assumed that an AE which was reported to have started on Cycle 1, Day 1 without an associated onset time occurred on or after initiation of study drug. Treatment-emergent serious adverse events (TESAEs) are collected through 90 days post last dose of study drug.

Adverse Event of Special Interest (AESI)

Any AE (serious or non-serious) of scientific and medical concern for which ongoing monitoring and communication by the investigator to the Sponsor or designee may be appropriate. Such events may require further investigation to characterize and understand them.

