4.3. SAFETY

Participants receiving at least one lerapolturev injection. If a participant crosses over from monotherapy to combination therapy, then the treatment analyzed will be based on the treatment for that participant at the time of the assessment.

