5.7. SAFETY

Participants receiving at least one lerapolturev injection will be analyzed for safety. Values for all safety variables will be listed by participant and visit (as applicable). Safety summaries by visit will use scheduled visits up to 30 days after the last dose of study drugs.

If a participant crosses over from monotherapy to combination therapy, then the treatment analyzed will be based on the treatment for that participant at the time of the assessment.

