5.7.1. Adverse Events

AE will be mapped to a MedDRA version 24.0 by SOC and PT. If a participant experiences multiple events that map to a single PT, the greatest severity and strongest assessment of relation to a study drug will be assigned to the PT for the appropriate summaries. AE severity will be assessed according to the NCI CTCAE version 5. If CTCAE grading does not exist for an AE, the severity of the AE will be graded as mild (1), moderate (2), severe (3), life-threatening (4), or death (5).

AESIs will be identified within the EDC by the investigator.

The number of participants for the following groups will be summarized by treatment group and overall:

- Any TEAE
- Any TEAE related to
 - o lerapolturev

- o anti-PD-1 therapy
- Any TESAE
- Any TESAE related to
 - o lerapolturev
 - o anti-PD-1 therapy
- Any treatment-emergent lerapolturev AESIs
- Any treatment-emergent irAEs
- Any TEAE with CTCAE grade ≥ 3
- Any TEAE related to
 - o lerapolturev with CTCAE grade ≥ 3
 - o anti-PD1 therapy with CTCAE grade ≥ 3
- Any Grade 5 TEAE
- Any Grade 5 TEAE related to lerapolturev or anti-PD1 therapy

The occurrence of TEAEs and TEAEs related to lerapolturev, or anti-PD-1 therapy will be summarized by PT, SOC, and severity. Additionally, TEAEs will be summarized by PT in descending frequency. All AEs reported will be listed for individual participants showing both verbatim and PT. All AEs that occurred prior to initiation of study drugs will be excluded from the tables but will be included in the listings.

Adverse events occurring during screening due to lerapolturev-related procedures that are not standard of care (eg, PV booster) will be considered related to lerapolturev and summarized separately.

Additional analysis may be conducted to investigate rates of TEAE based on lerapolturev dose and/or schedule. Should there be a difference, we may perform additional analyses to discern whether there is a relationship between dose and occurrence of AEs.

Missing onset dates will be imputed as previously outlined in Section 3.2.3.2 as required to determine TEAE.

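### Monotherapy safety follow-up closes at crossover while Arm 2 follow-up runs 30 days past the last dose, and SAP 5.7.1 plans only crude percentages with no adjustment for time at risk

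*SAP*

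**What the plan says.** - **Attribution.** SAP 4.3 and SAP 5.7 both place a crossing participant's safety data by current treatment: "then the treatment analyzed will be based on the treatment for that participant at the time of the assessment". Protocol Table 3 shows this in use. Its footnotes say of the monotherapy columns, "Data shown do not include data collected during crossover", and fix the boundary: "Crossover starts with first administration of first crossover cycle".
- **Window.** SAP 3.2.6: "A TEAE is an AE that occurred during the study on or after the initiation of study drug through 30 days after last dose of" the trial drugs. The same section has serious AEs, AESIs and irAEs collected to 90 days after the last dose.
- **Last dose.** Protocol 6.2 says "study drug administration may be continued until loss of clinical benefit", and does not restrict this to one arm. Under Protocol 5.3, Arm 2 participants continue anti-PD-1 if injections stop after a confirmed CR or once all injectable lesions have resolved.
- **Crossover.** Protocol 3.1.1 allows it, as an option, at unconfirmed RECIST progression, at week 26 without progression or confirmed PR, or after a PR of at least 6 months. By the December 2021 cutoff, "7 lerapolturev monotherapy participants crossed over to receive the lerapolturev/anti-PD-1 combination", out of 11 treated with monotherapy (Protocol 1.2.2.2).
- **Summary measure.** SAP 5.7.1: "The number of participants for the following groups will be summarized by treatment group and overall". SAP 5 defines categorical summaries as frequencies and percentages. Days on treatment (SAP 5.1) and cycles received (SAP 5.5) are summarised separately and are not used as a denominator for events. The optional further analysis in SAP 5.7.1 concerns lerapolturev dose and schedule, not the presence of anti-PD-1.

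**The concern.** The chance of having at least one event grows with time at risk. A crossing monotherapy participant contributes time only up to the first crossover dose. A matching Arm 2 participant, progressing at the same scan, contributes that time, plus any dosing past progression, plus the post-dose tail. If adding anti-PD-1 changed nothing, the Arm 2 percentage would still tend to be higher.

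Safety with and without anti-PD-1 is a primary objective, and the AE tables set these groups in adjacent columns. The sponsor already reads such columns this way: Protocol 1.3.1 cites Tables 3 and 4, which are crude percentages, when judging whether the combination raises the risk of cutaneous irAEs. A descriptive statement drawn from the final tables would mix a drug effect with a follow-up effect.

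**Working it through.** **1. The plan's own figures.** The documents give no figure for time at risk. Protocol Table 3 confirms the crude form for any AE: monotherapy 8/11 = 72.7%, Arm 2 2/6 = 33.3%, crossover 5/7 = 71.4%, all combination (2+5)/13 = 53.8%. All reproduce.

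**2. Inputs.** From the documents: a tail of 30/7 = 4.29 weeks (SAP 3.2.6), scans at weeks 6 and 12 and then every 12 weeks (Protocol Table 1), and a crossover share of 7/11 = 0.636. Assumed: the same constant weekly hazard *h* (0.02 or 0.04) in both arms; progression found at week *w* = 6/12/24/36 in 35/30/20/15%; crossover at progression; *b* = 0 or 6 weeks of treatment beyond progression for everyone who does not cross over.

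**3. Formula.** Risk over *x* weeks = 1 − exp(−*hx*). For crossing participants *x* = *w*. For Arm 2 and non-crossing monotherapy participants *x* = *w* + *b* + 4.29. Monotherapy arm = (7/11) × crossing + (4/11) × non-crossing. Loss = 1 − monotherapy/Arm 2.

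Example, *h* = 0.02, *b* = 0. Crossing: 0.35(1−e^−0.12) + 0.30(1−e^−0.24) + 0.20(1−e^−0.48) + 0.15(1−e^−0.72) = 25.7%. Arm 2: 31.8%. Monotherapy: (7/11)(25.7) + (4/11)(31.8) = 27.9%. Loss: 1 − 27.9/31.8 = 12%.

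| *h* | *b* | Crossing | Arm 2 (= non-crossing) | Monotherapy arm | Gap, points | Loss |
|---|---|---|---|---|---|---|
| 0.02 | 0 | 25.7% | 31.8% | 27.9% | 3.9 | 12% |
| 0.04 | 0 | 42.7% | 51.7% | 46.0% | 5.7 | 11% |
| 0.02 | 6 | 25.7% | 39.5% | 30.7% | 8.8 | 22% |
| 0.04 | 6 | 42.7% | 62.0% | 49.7% | 12.3 | 20% |

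**4. Real dose timing.** Step 3 treats the last dose, progression and crossover as simultaneous, so it removes a full 30 days. Under Protocol Table 1 the gap between the last monotherapy dose and the first crossover dose still counts as monotherapy. Take no dose on the scan day, crossover at the next scheduled dose, and *b* = 0:

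| Scan | Last dose | Crossing window | Arm 2 window | Share lost |
|---|---|---|---|---|
| Week 6 | Day 36 | 42 days | 36+30 = 66 | 24/66 = 36% |
| Week 12 | Day 64 | 84 | 64+30 = 94 | 10/94 = 11% |
| Week 24 | Day 148 | 168 | 148+30 = 178 | 10/178 = 6% |
| Week 36 | Day 232 | 252 | 232+30 = 262 | 10/262 = 4% |

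With these windows in the step 3 formula, *h* = 0.02 gives 26.9% against 29.0% and *h* = 0.04 gives 44.6% against 47.9%. The loss is 7% in both.

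**5. Sensitivity.**
- No crossover: the windows match and the gap is zero.
- Front-loaded events: take cumulative hazard A(1−e^(−t/2)) with 60% affected by week 26, so A = 0.916. By week 6 the risk is 1 − exp(−0.916 × 0.950) = 58.1%, against at most 60.0% with a longer window. That is under 2 points even for a participant crossing at week 6.
- 90-day window (serious AEs, AESIs, irAEs, if the tables use it): the tail is 90/7 = 12.86 weeks. At *h* = 0.02, *b* = 0, Arm 2 is 42.5% and monotherapy is (7/11)(25.7) + (4/11)(42.5) = 31.8%, a loss of 25%.
- The week-26 crossover route is not modelled. It would shorten the monotherapy window further.

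**6. Does person-time remove it?** Under a constant hazard, expected time at risk to first event is risk/*h*. At *h* = 0.02, *b* = 6: Arm 2 0.395/0.02 = 19.75 weeks, monotherapy 0.307/0.02 = 15.35 weeks. Both give 2.0 first events per 100 participant-weeks. A separate equal-hazard simulation, with median progression of 12 weeks and half the participants treated 0, 6 or 12 weeks beyond it, had crude gaps of 3.7 to 10.0 points at 64% crossover. The ratio of person-time rates was between 0.998 and 1.003 in every setting.

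**The case against.** **The attribution rule is sound.** A reader might infer that closing the monotherapy column at crossover is itself the error. It is not: it keeps events under anti-PD-1 from being credited to monotherapy, and the remedy below censors at the same point. What is missing is the denominator. This stands.

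**No formal comparison exists.** A reader might infer that a primary between-arm safety test is biased. The objective is to evaluate safety with and without anti-PD-1. Protocol 8.3 mentions arm comparisons in the sample-size section for ORR and says no formal hypothesis will be tested. SAP 5 is descriptive throughout. This stands and limits the point to how descriptive tables are read.

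**Unequal follow-up is visible.** Crossover participants have their own column, and days on treatment and cycles are reported. True, but visibility is not adjustment.

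**The inputs are soft.** The 7/11 share comes from the Q3/4W schedule, includes the safety run-in and predates the eligibility changes. The QW share is unknown. Many events may cluster in the weekly induction, where the bias is small. Continued anti-PD-1 after injections stop requires a confirmed CR or resolution of injectable lesions, and the best response at the cutoff was stable disease, so that route may add little. All of this stands. It affects size, not direction.

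**Table 3 shows the opposite order** (8/11 against 2/6, Fisher p = 0.16). Follow-up times are not given, so it neither refutes nor supports the point.

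**Conclusion.** The point holds as a gap in the summary measure. With equal hazard and equal progression, no Arm 2 window is shorter than the matching monotherapy window, and it is longer wherever the first crossover dose comes before the Arm 2 window would close. The planned percentages therefore tend to overstate Arm 2 toxicity relative to monotherapy.

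Size, with 7/11 crossing over and a constant hazard of 0.02 to 0.04 per week: about 7% to 12% of monotherapy participants with events are lost without treatment beyond progression, and about 20% to 22% with 6 weeks beyond it for all who do not cross over. It is at most about 2 points if events are front-loaded, zero without crossover, and larger for serious AEs, AESIs and irAEs if their tables use 90 days.

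Two stronger readings are not supported. First, a loss of 29% (27.9% against 39.5% at hazard 0.02) appears only if Arm 2 alone is treated beyond progression; Protocol 6.2 has no such limit. Second, a reader might extend the direction to the pooled column of all lerapolturev + anti-PD-1 participants. It is not fixed there. With 20% affected by week 26, *h* = −ln(0.8)/26 = 0.0086. A 6-week crossover phase plus 30 days then gives 1 − exp(−0.0086 × 10.29) = 8.4%, below the 20.0% of a 26-week monotherapy window.

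**What to change.** In SAP 5.7.1, keep the crude tables and add the following for the main rows (any TEAE, Grade 3 or higher, serious, irAE, related):

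1. **Exposure-adjusted incidence:** participants with a first event per 100 participant-weeks. At-risk time runs from C1D1 to the earliest of first event, first crossover dose, or the end of that row's reporting window (last dose + 30 days, or + 90 days where that window is used). State which rows use which window.
2. **Onset-date rule:** assign events around crossover by onset date, replacing the looser reference to the time of assessment.
3. **Supportive common-window table:** events with onset in Days 1 to 42, censored at any earlier crossover. The censoring is needed because Protocol Table 6 provides for crossover during weekly injections.

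Base any descriptive Arm 1 versus Arm 2 safety statement on these summaries.

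Cost: SAP wording and two extra tables from dates already collected. The rates assume a roughly constant hazard and will be imprecise at about 15 participants per arm. The 6-week table misses late events, which is one reason to keep the crude tables.

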4.4. SCREENING ANALYSIS SET

A screening analysis set will include all participants who signed the ICF and includes screen failures who failed up until randomization. This will be the primary population for the disposition tables and listings. Participants in the screening analysis set will be analyzed based on the treatment assigned.

5. STATISTICAL METHODS

Descriptive statistical methods will be used to summarize the data from this study. Unless stated otherwise, the term "descriptive statistics" refers to number of participants (n), mean, median, standard deviation, minimum and maximum for continuous data and frequencies and percentages for categorical data.

Survival endpoints will be analyzed with Kaplan-Meier method and summarized with median, twenty-fifth and seventy-fifth percentiles, and 95% confidence intervals (CI), if applicable.

All data collected during the study will be included in data listings. Unless otherwise noted, the data will be sorted first by treatment, participant, and then by date within each participant number.

All summary tables and figures will be presented by treatment group and overall. The term "treatment group" refers to the following subgroups:

- lerapolturev monotherapy on the QW schedule
- lerapolturev monotherapy on the Q3/4W schedule
- lerapolturev + anti-PD-1 on the QW schedule
- lerapolturev + anti-PD-1 on the Q3/4W schedule
- all crossover to lerapolturev + anti-PD-1 participants
- lerapolturev + anti-PD-1 plus crossover participants (all lerapolturev + anti-PD-1)
- overall treated participants

Analyses will be implemented using SAS® 9.4 or higher (SAS Institute, Cary, North Carolina, USA). The International Conference on Harmonization (ICH) numbering convention (ie, ICH-E3) will be used for all tables and listings. Upon completion, all SAS® programs will be validated by an independent programmer within the staff of the third-party vendor doing the primary analysis. The validation process will be used to confirm that statistically valid methods have been implemented and that all data transformations and calculations are accurate. Checks will be made to ensure accuracy, consistency with this plan, consistency within tables, and consistency between tables and corresponding data listings. All documents will be verified by the lead statistician to ensure accuracy and consistency of analyses.

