Statistical Methods	The primary endpoint for measuring anti-tumor activity will be ORR, based on RECIST 1.1, which will be summarized as the overall number (%) of participants with CR or PR in each treatment arm, along with 95% confidence interval (CI). Participants will be analyzed based on the treatment arm to which they were randomized, as well as by lerapolturev dose/schedule (ie, QW and Q3/4W). Other endpoints will be summarized by descriptive statistics, as appropriate. Further details for these and other analyses will be described in the statistical analysis plan (SAP).
Determination of Sample Size	Sample size was determined based on feasibility and logistical considerations. Based on an estimated sample size of 15 participants in Arm 2 receiving lerapolturev QW in combination with anti-PD-1, five objective responses are needed for the 95% confidence interval (CI) to be above 10% (33% ORR; 95% CI: 11.8% to 61.6%), which would indicate the combination has antitumor activity in this anti-PD-1 resistant population. See Section 8.3 for additional details regarding sample size determination.
Study Duration	Up to approximately 24 months (104 weeks)

Confidential Page 18 of 109

^Criteria for Crossover

- radiologic disease progression per RECIST v1.1 (progression does not need to be confirmed prior to crossover)
- has not had progression or confirmed partial response per RECIST v1.1 by week 26 on study
- partial response ≥ 6 months in duration

Confidential Page 19 of 109

Table 1. Schedule of Assessments for Lerapolturev Monotherapy or Lerapolturev + Pembrolizumab

NOTE: Cycle length for lerapolturev monotherapy or lerapolturev + pembrolizumab is 3 weeks. Lerapolturev is administered weekly during Cycles 1 & 2 and every 3 weeks thereafter on the days indicated in the table below. Refer to the table below for the timing of other study assessments to be completed within each cycle.

	Screening Period	o		EOT Visit ¹⁵	Survival Follow- up ¹⁶	
Study Procedure ³		Cycle 1	Cycle 2	≥ Cycle 3		
	(≤ 28D prior to C1D1)		+3W (+7D)	Q3W (+7D)	≤28D after last treatment	
Informed Consent ¹	X					
Medical History	X					
Physical Exam ^{2,3}	X	C1D1	C2D1	Day 1 of each Cycle	X	
Vital Signs ³	Х	C1D1, C1D8, C1D15	C2D1, C2D8, C2D15	Day 1 of each Cycle	X	
ECOG Performance Status ³	Х	C1D1	C2D1	Day 1 of each Cycle	Х	
PV Immunization Booster ¹	≥1W, but ≤6W before C1D1					
Adverse Events		Conti	Continuous from signing ICF until 30 days after last dose of study therapy			

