4.2. EFFICACY

Participants receiving at least one lerapolturev injection and at least 1 post-baseline assessment. If a participant crosses over from monotherapy to combination therapy, then the treatment analyzed will be based on the treatment for that participant at the time of the assessment for the efficacy set.

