5.6. EFFICACY

5.6.1. Primary Efficacy Endpoints

The primary efficacy endpoint is ORR which is the overall number and percentage of participants in each treatment arm with confirmed CR or confirmed PR. The primary analysis for the safety run-in and Arm 1 will include participant response prior to crossover to Arm 2. ORR will be analyzed by treatment arm, dosing schedule and overall.

CONFIDENTIAL Page 26 19 November 2024

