7. CHANGES IN THE PLANNED ANALYSES

The following exploratory analysis listed in protocol will no longer be conducted.

- ORR/DOR, DRR, DCR, and DCR-6mo based on iRECIST criteria
- ORR, DOR, DRR, DCR, and DCR-6mo in the following subgroups:
 - o Acquired versus primary PD-1/L1 resistance, as defined by Kluger, et al
 - o BRAF wild type and mutant
 - o LDH levels at baseline
 - \circ Time since last dose of anti-PD-1/L1 therapy prior to randomization (\le or > 6 weeks)
 - o Crossover to combination arm from lerapolturev monotherapy
- OS and PFS in the following subgroups:
 - o According to treatment arm and AJCC stage at baseline
 - o Acquired versus primary PD-1/L1 resistance, as defined by Kluger, et al
 - o BRAF wild type and mutant
 - o LDH levels at baseline
 - \circ Time since last dose of anti-PD-1/L1 therapy prior to randomization (< or > 6 weeks)
 - o Crossover to combination arm from lerapolturev monotherapy

8. REVISION HISTORY

Date	Revision	Rationale
10OCT2024	 Update PFS definition to be censored at last imaging instead of death. Update tables that were using the ITT Population to Safety Population. 	 Last imaging is more appropriate here since we are looking at Progression-free Survival. ITT does not include Safety Run-ins since those subjects are not randomized.

9. REFERENCES

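### On the Q3/4W schedule the SAP pools the six non-randomised run-in participants with Arm 1, so no planned summary table shows the randomised Arm 1 versus Arm 2 comparison

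*SAP*

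**What the plan says.** SAP Section 5 sets the layout: "All summary tables and figures will be presented by treatment group and overall". It then lists seven groups, which also appear in SAP 3.2.1. Four are defined by regimen and schedule, among them "lerapolturev monotherapy on the Q3/4W schedule". Two concern crossover, and one is everyone treated. Neither the safety run-in nor Arm 1 has a group of its own.

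The analysis sets do not ask for randomisation. The Safety set (SAP 4.3) is "Participants receiving at least one lerapolturev injection", and the Efficacy set (SAP 4.2) is "Participants receiving at least one lerapolturev injection and at least 1 post-baseline assessment". The SAP's revision history records that tables were moved from the ITT to the Safety population, giving as the reason: "ITT does not include Safety Run-ins since those subjects are not randomized". For the response rate, SAP 5.6.1 adds: "The primary analysis for the safety run-in and Arm 1 will include participant response prior to crossover to Arm 2".

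The Protocol Synopsis, under Statistical Methods, says: "Participants will be analyzed based on the treatment arm to which they were randomized". The same sentence adds analysis by dose and schedule. Protocol 8.3 names Arm 1 versus Arm 2 among the additional planned comparisons, without a formal test. Protocol Tables 3 and 4 give the run-in, Arm 1 and all monotherapy participants separate columns.

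**The concern.** The 1:1 allocation is what makes monotherapy and combination comparable. The run-in stands outside it. Those participants were enrolled before the randomised part opened, the run-in was complete by July 2021 (Protocol 3.1), and they were not covered by the stratification applied to randomised Q3/4W participants. If they share a column with Arm 1, a reader who sets that column beside Arm 2 is comparing a mixed, partly earlier cohort with the combination arm.

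Safety with and without anti-PD-1 is a primary objective, and the planned analysis is descriptive. In such an analysis the column definitions decide what can be read. At stake is whether the final Q3/4W tables allow the randomised contrast to be seen at all.

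**Working it through.** **1. Where the run-in participants fall.**
- Protocol 3.1 and 3.1.3: six participants, lerapolturev monotherapy, Q3/4W schedule, before randomisation began.
- SAP 4.2 and 4.3: entry depends on an injection (plus one post-baseline assessment for efficacy), so they qualify.
- SAP 5: until a participant crosses over or takes the optional QW switch, the only groups that fit are Q3/4W monotherapy and overall.
- SAP 11: the disposition table uses the Screening set; every other summary table and figure uses Safety or Efficacy. The ITT set is defined in SAP 4.1 but appears in no table, figure or listing title.

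No SAP sentence states the merge. It is the only result of applying the group list and set definitions as written.

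**2. Share of the column.** At the 10 December 2021 cut (run-in 6, Arm 1 5): 6/(6+5) = 54.5%. With six per randomised arm, the count given in Protocol 9.1.5: 6/(6+6) = 50%.

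**3. Reproducing the protocol's pooled figure.** Treatment-related adverse events in Protocol Table 3: (4+1)/(6+5) = 5/11 = 45.5%, which matches the all-monotherapy column.

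**4. Effect of the column definition.** Counts are from Protocol Table 3. Difference = monotherapy % minus Arm 2 %.

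| Row | Run-in | Arm 1 | Merged | Arm 2 | Difference, randomised | Difference, merged |
|---|---|---|---|---|---|---|
| Treatment-related AE | 4/6 | 1/5 (20.0%) | 5/11 (45.5%) | 2/6 (33.3%) | -13.3 | +12.1 |
| Grade 3 or 4 AE | 2/6 | 0/5 (0.0%) | 2/11 (18.2%) | 1/6 (16.7%) | -16.7 | +1.5 |
| Any AE | 6/6 | 2/5 (40.0%) | 8/11 (72.7%) | 2/6 (33.3%) | +6.7 | +39.4 |
| Lerapolturev-related AE | 4/6 | 1/5 (20.0%) | 5/11 (45.5%) | 1/6 (16.7%) | +3.3 | +28.8 |
| Serious AE | 0/6 | 0/5 (0.0%) | 0/11 (0.0%) | 1/6 (16.7%) | -16.7 | -16.7 |

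Two rows change sign, two keep their sign but grow, and one does not move.

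**5. Precision.** For treatment-related events the Clopper-Pearson 95% intervals are 0.5 to 71.6% (Arm 1), 16.7 to 76.6% (merged) and 4.3 to 77.7% (Arm 2). Fisher's exact p against Arm 2 is 1.0 for Arm 1 and 1.0 for the merged column. Run-in against Arm 1 gives p = 0.24.

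**6. The success criterion.** SAP 3.1 requires 5 of 15 responders in Arm 2 on QW. Clopper-Pearson for 5/15 is 11.8 to 61.6%, as stated, and 4/15 gives a lower bound of 7.8%. The Q3/4W monotherapy column does not enter.

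**The case against.** **Grouping by schedule is the protocol's own.** Protocol 8.4 defines Q3/4W safety and efficacy populations by receipt of an injection, so the run-in is already inside them, and Protocol 8.5 lets the SAP prevail where the two differ. This stands as far as it goes: pooling for a schedule-level summary is legitimate. But the protocol also asks for analysis by randomised arm, and the SAP's groups provide only the schedule view on Q3/4W.

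**SAP 5.6.1 names the run-in and Arm 1 and promises the response rate by treatment arm.** The table shells are not in the documents, so separate columns might still be produced. The group list in SAP 5 does not provide them, however, and it governs all summary tables and figures.

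**The sign changes rest on single events.** One more treatment-related case in Arm 1 would make it 2/5 = 40.0%, above Arm 2's 33.3% with no run-in data involved. One Grade 3 or 4 case would give 1/5 = 20.0%, above 16.7%. Table 3 is also an interim cut without exposure time, and the run-in started earlier, so the cohort gap may reflect longer time at risk. All of this stands. A reader might infer that merging reverses the trial's safety comparison, or misstates what adding anti-PD-1 does. The documents do not support that: the reversal appears in two of the five rows examined, and final-analysis data may look different.

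**Efficacy is not shown to be distorted.** Protocol 1.2.2.2 reports stable disease as the best response at that cut, so the response rate was zero in every group and pooling changed nothing. No PFS or OS figures are given. This stands.

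**Splitting out the run-in is not sufficient.** Q3/4W participants could move to QW, and the SAP does not say which column then holds them. This also stands, so the new columns need an as-randomised definition.

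**Conclusion.** The point holds for the Q3/4W schedule. Following the SAP exactly, six non-randomised participants, about half of the monotherapy column (6/11 at the December 2021 cut), are pooled with Arm 1, and no planned summary table lets the protocol's Arm 1 versus Arm 2 comparison be read from randomised participants. Protocol Table 3 shows that the choice of column can change a descriptive reading by about 25 points for treatment-related events (from -13.3 to +12.1) and about 18 points for Grade 3 or 4 events (from -16.7 to +1.5).

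Those figures illustrate sensitivity to the definition. They are not estimates of effect and give no evidence that the run-in and Arm 1 truly differ. A reader might also infer that the trial's main conclusion is compromised. It is not: the arm comparisons carry no formal test, and the only success criterion uses Arm 2 on QW. QW monotherapy is affected only if a run-in participant switched to that schedule while on monotherapy. The change is worth making because it is a grouping rule that departs from a stated protocol analysis and is easily corrected.

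**What to change.** In SAP 3.2.1 and 5, replace the single Q3/4W monotherapy group with two: safety run-in (non-randomised) and Arm 1 Q3/4W (as randomised). Keep the pooled monotherapy column as an additional total labelled non-randomised, following Protocol Tables 3 and 4. State that Arm 1 versus Arm 2 is read only from the randomised columns, with Arm 2 Q3/4W defined on the same as-randomised basis. Apply the same separation to any run-in participant who switched to QW, so that the QW monotherapy column is not mixed in turn.

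The cost is SAP wording and one more column, with smaller counts in each. The layout already exists in the protocol, no new data are needed, and no information is lost because the pooled total remains.
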